**Form A**

IRB #	STU -----
-------	-----------

#### 1. Purpose and objectives. *List the purpose and objectives:*

The overarching goal of this pilot prospective randomized controlled study is to compare patient-reported and clinical operations outcomes between in-person genetic counseling (IPGC – control) and telephone-based genetic counseling (TGC – intervention) in an indigent English or Spanish-speaking population seeking genetic counseling for hereditary cancer syndromes to create a framework for effective and efficient genetic service delivery in these populations nationally. General genetic education and principles will be conveyed through a standard genetic counseling session including a pre-test education video in both the TGC and IPGC arms. Our primary project objectives are to compare the following outcomes between the IPGC and TGC study arms. Aim 1: Patient reported outcomes – A. Patient satisfaction with genetic counseling visit; B. Knowledge of basic principles of cancer genetics and implications of genetic testing for personal healthcare and relatives. Secondary objectives for this aim are: 1. Patient ability to make informed choice; and 2. Genetic counseling-specific empowerment outcomes. Aim 2: Clinical outcomes – visit completion rate; Secondary objectives are: 1. Genetic testing completion rate; and 2. Genetic testing cancellation/failure rate. We hypothesize that patients in the TGC arm will not have significant differences in knowledge, satisfaction, informed choice or genetic counseling-specific empowerment compared to the IPGC arm. We also expect significantly increased visit completion rate and lower test completion rate in the TGC arm compared to the IPGC arm, but no significant difference in sample failure rate.

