##### a. Background

Similar studies have been performed in primarily non-Hispanic white, above-average income, college-educated, English-speaking populations, but to our knowledge, a study comparing outcomes of TGC and IPGC service delivery models (SDMs) has not been reported in an entirely indigent population with a high volume of Latinx/Spanish-speaking patients. Indigent Populations. Less access to healthcare and hereditary risk assessment are well documented in indigent populations, often composed of ethnic/racial minorities, or geographically isolated and economically underserved groups. 7-9 Barriers include provider paucity, under-recognition of family history risk factors, financial hardship, and other factors. 10- 17 Internet use via mobile technologies has increased access to healthcare information in indigent populations .18, 19 National surveys revealed 91% of families living below the poverty level have some type of internet access, and of Americans earning <\$30,000 annually, 701% owned a smart phone. Review of 2019 internal program data revealed 84-88% of safety-net hospital clinic uninsured/Medicaid patients provided an email address and reported internet connectivity. This access creates an avenue for genetic counselors to reach underserved populations. Genetic Counseling Service Delivery. Some randomized trials comparing outcomes of TGC v. IPGC cancer risk assessment sessions in resource-rich populations showed similar levels of patient satisfaction, knowledge, cancer worry, risk perception, decisional conflict, and motivation to change health-related behavior with similar data for telegenetics (video) studies. In one study, the majority of participants indicated they would not have pursued genetic counseling had TGC not been offered. Need for Project. A majority (89%) report already using a phone for medical discussions. Traditional healthcare infrastructures remain a barrier for indigent patients, and while the rise in telegenetics companies and platforms in a response to the increasing need for remote genetic counseling to

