Data Analysis. Our primary study outcomes are to compare change in knowledge pre and post visit (through MMIC knowledge questions), patient satisfaction with GC visit after completion (GCSS) and genetic counseling visit completion rate between IPGC and TGC. Secondary objectives include comparison of empowerment score (GCOS), informed choice (MMIC scale), genetic testing completion, and cancelation/failure rates between the arms.

To evaluate intervention effects, we will conduct univariable and multivariable analysis for comparisons of each outcome of interest between intervention (TGC) and control group (IPGC). For the survey data, we will examine the data from each survey as well as total score or overall index of multiple questionnaires and compare them between the two study arms. We will perform linear regression models for continuous outcomes (e.g., total score of questionnaires) and logistic regression models for binary outcomes that are based on binary response (e.g., visit completion rates, test cancelation/failure and test completion rates). To compare binary outcomes between arms (such as visit completion rate), we will test by comparing rates of each arm via Chi-squared analysis and control for potential confounders. Potential covariates under consideration (e.g., age, race, sex, language, etc.) will be assessed as necessary and adjusted in multivariable models accordingly. We will evaluate whether there is any evidence of multi-collinearity issues among these variables to be adjusted in the model. Possible effect modifiers of intervention effects will be also evaluated by testing interactions (e.g., sex) and addressed to develop the final multivariable models, as well as reporting the intervention effect stratified as an effect modifier. Underlying assumptions of aforementioned regression models including linearity of associations will be also evaluated. We will examine dropouts or missing data to be able to identify accurate missing data mechanisms and select the best statistical approach. All analyses will be performed using SAS 9.4 (SAS Institute Inc, Cary, NC) at a statistical significance level of  $p=0.05$ .

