We anticipate a post-enrollment dropout (failure to complete the surveys) rate of 30% given our work with the underserved population. We plan to enroll 280 patients at a 1:1 ratio per arm (100 individuals enrolled per arm), expecting 200 to complete measured responses. We will monitor the dropout rate after the initial 50 individual responses are completed and adjust accrual for study-specific dropout until we have 200 participants' complete measured responses. With 200 patients we will enroll, we can detect mean differences of 0.398 standard deviation (SD) between two study arms with 80% power at a significance level of 0.05 (Table 1). For example, assuming SD of 2 for the GCSS, we will be able to detect a minimum difference of 0.8 ( $=0.398*2$ ) between two study arms with 100 participants enrolled per arm. For GCOS, assuming SD of 46.58, we will be able to detect a minimum difference of 18.54 between pre- and post-visit scores. For visit completion as the primary binary outcome variable, we will be able to detect a minimum difference of 18.6% assuming 63% in the control group, e.g., 81.6% (intervention) vs. 63% (control) with 80% power at significance level of 0.05. Of note, previously published outcomes and unpublished internal data will serve as a baseline for the study population.

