**Form A**

IRB #	STU -----
-------	-----------

*Table 1.* Summary of instrumentation with objectives, measures and distribution plan. Summary of data analysis plan per primary and secondary objectives. Minimum detectable difference between two study arms with 80% power at 2-sided significant level of 0.05 (n=100 per arm)

Aims	Objective Type	Instrumentation	Outcome Measure	Distribution	Minimum Detectable Effect Size at 80% power
Aim 1: Patient Satisfaction	Primary	GCSS	Whole scale score	Post	+/-0.8 points, assuming SD = 2 
Aim 1: Knowledge	Primary	MMIC (8 knowledge questions)	Measure score difference from pre/post	Pre and Post	+/-2 points, assuming SD = 5.03
Aim 1: Informed Decision Making	Second	MMIC (entire measure)	Measure score difference from pre/post	Pre and Post	n/a
Aim 1: GC-specific empowerment	Second	GOS	Measure score difference pre/post	Pre and Post	+/-18.54 points, assuming SD = 46.58 
Aim 2: GC visit completion	Primary	Database query	Proportion of visits scheduled and completed	n/a	18.6%, assuming 63% in control group 
Aim 2: Genetic test completion	Second	Database query	Proportion of genetic tests completed w/n 60d of visit	n/a	19.4%, assuming 77.4% in control group 
Aim 2: Genetic test cancellation/failure	Second	Database query	Proportion of genetic tests initiated compared to tests canceled/failure	n/a	15%, assuming 9% in control group 

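### The hypothesis of no significant difference for satisfaction and knowledge is met by p>0.05, which does not show that the arms are similar, and the plan has no rule for reading such a result

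*Combined protocol and SAP*

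**What the plan says.** Section 1 (Purpose and objectives) names satisfaction, knowledge and visit completion as primary. For the patient-reported outcomes it states: "We hypothesize that patients in the TGC arm will not have significant differences in knowledge, satisfaction, informed choice or genetic counseling-specific empowerment". For the laboratory outcome it expects differences in visit and test completion, "but no significant difference in sample failure rate".

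The Data Analysis text in section 4.a plans linear regression for scores and logistic regression for binary outcomes. For rates, "we will test by comparing rates of each arm via Chi-squared analysis". The significance level is 0.05.

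The sample-size paragraph that follows is written for a difference test: "we can detect mean differences of 0.398 standard deviation (SD) between two study arms with 80% power". Table 1 turns this into detectable differences at 100 per arm and a two-sided 0.05 level: 0.8 points for satisfaction (GCSS, SD 2), 2 points for knowledge (SD 5.03) and 18.54 points for empowerment (SD 46.58). For test cancellation or failure the entry is "15%, assuming 9% in control group". Informed choice has no entry.

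Nothing in the document gives an equivalence or non-inferiority margin, an interval criterion, or a statement of how a non-significant result will be interpreted.

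**The concern.** The hypothesis is phrased as the outcome of a significance test, and the result that fulfils it is the one that says least. A non-significant test does not separate arms that are close from arms that were measured too imprecisely. If a true deficit exists, noisier data make the hypothesized result more likely.

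What is at stake is the conclusion on two of three primary outcomes. As written, a result compatible with a deficit larger than the trial was sized to detect would agree with the stated hypothesis. The third primary outcome, visit completion, has a superiority hypothesis and is not affected.

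**Working it through.** **Inputs.** From section 4.a and Table 1: 100 per arm, two-sided 0.05, detectable difference 0.398 SD, and SDs of 2 (GCSS), 5.03 (knowledge) and 46.58 (empowerment). The comparison is taken as unadjusted.

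**Step 1: reproduce the plan's figure.** In SD units the standard error of the difference is √(2/100) = 0.1414. The critical t on 198 degrees of freedom is 1.972. At 0.398 SD the noncentrality is 0.398/0.1414 = 2.81, and the noncentral t gives power 0.800. In points: 0.398 × 2 = 0.80, 0.398 × 5.03 = 2.00, 0.398 × 46.58 = 18.54. The stated figures reproduce, which confirms that the sizing is for a two-sided difference test.

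**Step 2: how often p>0.05 occurs.** This is 1 minus power at each true difference, with 100 per arm:

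| True difference (SD) | GCSS points | Knowledge points | P(p>0.05) |
|---|---|---|---|
| 0 | 0 | 0 | 95% |
| 0.2 | 0.4 | 1.0 | 71% |
| 0.3 | 0.6 | 1.5 | 44% |
| 0.398 | 0.8 | 2.0 | 20% |

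**Step 3: precision.** The 95% CI half-width is 1.972 × 0.1414 = 0.279 SD. That is 0.56 GCSS points, 1.40 knowledge points and 12.99 empowerment points.

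**Step 4: how often a null result would leave the question open.** Suppose there is no true difference. The result is non-significant, yet its interval reaches a telephone-arm deficit beyond 0.398 SD, when the estimate lies between −0.279 and −(0.398 − 0.279) = −0.119 SD.

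- P(estimate below −0.119) = P(Z < −0.119/0.1414) = P(Z < −0.842) = 0.200.
- P(estimate significantly negative) = 0.025.
- Difference: 0.200 − 0.025 = 0.175.

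Simulation with the SD estimated rather than known gives the same 17.5%. The corresponding figure for an interval reaching beyond 0.5 SD is about 3.4%.

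**The case against.** The strongest reply is that no misuse is planned. The study calls itself a pilot, its objective is to compare, and it never claims equivalence or non-inferiority. Read literally, the hypothesis concerns significance, and the planned test settles that. Table 1 already gives a benchmark for reading a null result, and the planned regressions yield estimates from which intervals follow. Some of the numbers above are also just design properties: 20% at 0.398 SD is one minus the stated power, and 95% at zero is one minus alpha.

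Much of this stands, and it limits the point. A reader might infer any of the following, which the document does not support:

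- **That the trial will report p>0.05 as similarity.** It does not say so. The Background section does say that some earlier randomized trials "showed similar levels of patient satisfaction, knowledge, cancer worry, risk perception, decisional conflict", but that describes other studies.
- **That this is a failed equivalence design or an inadequate sample size.** No equivalence aim is stated, and the sizing is right for the test it describes.
- **That fewer completers should be assumed.** Section 4.a plans to continue accrual until 200 complete responses are in hand, so figures for smaller arms would not describe the plan.
- **That a null result will typically allow a deficit of 0.56 SD.** That limit (2 × 0.279) applies only to an estimate at the edge of significance. Step 4 gives the frequency of the broader problem.

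What the reply does not remove is the mismatch. The plan sets out an expected result for primary outcomes, p>0.05 meets it, and nothing commits the team to report the interval that would show what was ruled out.

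**Conclusion.** The point holds as a mismatch between hypothesis and test, together with a missing rule for interpretation. It affects two of the three primary outcomes directly and three secondary ones by the same wording. Its size at the planned 100 per arm is a 44% chance of the hypothesized result at a true 0.3 SD deficit and 20% at 0.398 SD. With no true difference, there is a 17.5% chance of a null result that fails to exclude a deficit above the plan's own detectable difference. These figures assume unadjusted comparisons, equal arms and the plan's SDs.

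The comparison itself remains valid, and no redesign is called for. The wording should be settled before outcome data are seen.

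**What to change.** 1. In the Data Analysis text of section 4.a, add: *For satisfaction, knowledge change, informed choice, empowerment change and sample failure, the TGC minus IPGC difference will be reported with its 95% CI; p>0.05 will not be interpreted as similarity.* For sample failure, take the difference in proportions from the 2×2 table, since logistic regression gives odds ratios.
2. In section 1, reword the hypothesis to match, for example: *We expect small differences, which will be estimated with 95% CIs.*

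Enrolment, models, the stated detectable differences and the superiority test for visit completion stay as they are. The cost is that the trial gives up any similarity claim based on p>0.05. If the sponsor wants a positive claim of non-inferiority or equivalence, a margin must be fixed and clinically justified before data are seen, and power restated against it. The document gives no margin, and this review does not suggest one.

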#### 2. Background.

- Describe past experimental and/or clinical findings leading to the formulation of your study.
- For research involving investigational drugs, describe the previously conducted animal and human studies.
- For research that involves FDA approved drugs or devices, describe the FDA approved uses of this drug/device in relation to your protocol.
- Attach a copy of the approved labeling as a product package insert or from the Physician's Desk Reference.

You may reference sponsor's full protocol or grant application (section number and/or title) or if none, ensure background includes references.

Please respond to all components of this item, or clearly indicate which components are not applicable.

##### a. Background

Similar studies have been performed in primarily non-Hispanic white, above-average income, college-educated, English-speaking populations, but to our knowledge, a study comparing outcomes of TGC and IPGC service delivery models (SDMs) has not been reported in an entirely indigent population with a high volume of Latinx/Spanish-speaking patients. Indigent Populations. Less access to healthcare and hereditary risk assessment are well documented in indigent populations, often composed of ethnic/racial minorities, or geographically isolated and economically underserved groups. 7-9 Barriers include provider paucity, under-recognition of family history risk factors, financial hardship, and other factors. 10- 17 Internet use via mobile technologies has increased access to healthcare information in indigent populations .18, 19 National surveys revealed 91% of families living below the poverty level have some type of internet access, and of Americans earning <\$30,000 annually, 701% owned a smart phone. Review of 2019 internal program data revealed 84-88% of safety-net hospital clinic uninsured/Medicaid patients provided an email address and reported internet connectivity. This access creates an avenue for genetic counselors to reach underserved populations. Genetic Counseling Service Delivery. Some randomized trials comparing outcomes of TGC v. IPGC cancer risk assessment sessions in resource-rich populations showed similar levels of patient satisfaction, knowledge, cancer worry, risk perception, decisional conflict, and motivation to change health-related behavior with similar data for telegenetics (video) studies. In one study, the majority of participants indicated they would not have pursued genetic counseling had TGC not been offered. Need for Project. A majority (89%) report already using a phone for medical discussions. Traditional healthcare infrastructures remain a barrier for indigent patients, and while the rise in telegenetics companies and platforms in a response to the increasing need for remote genetic counseling to

## Form A

IRB #	STU -----
-------	-----------

service under-resources and rural areas, outcomes of TGC in indigent populations have not been well-studied. Over 38 million people in the United States are considered low-income and are more likely to be patients in safety-net hospital systems, which necessitates optimization of genetic counseling SDMs in these cohorts. TGC, in particular, is critical to study in indigent populations given patient preference and accessibility to phone service. A UCSF study showed that indigent patients offered TGC versus video genetic counseling preferred the former and had an increased uptake of genetic counseling compared to other interventions.

Our study is not amenable to the following pieces of this question: *For research involving investigational drugs, describe the previously conducted animal and human studies. For research that involves FDA approved drugs or devices, describe the FDA approved uses of this drug/device in relation to your protocol. Attach a copy of the approved labeling as a product package insert or from the Physician's Desk Reference.*

### b. Current practice

n/a

### 3. Study Design.

[figure not shown]
Describe the study design (e.g., single/double blind, parallel, crossover, etc.) Consider inserting a scheme to visually present the study design.

This is a two-arm parallel randomized controlled study of IPGC vs. TGC with two enrolling sites.

**Form A**

IRB #

STU -----

## Form A

IRB # **STU -----**

### 4. Research Plan / Description of the Research Methods:

#### 4.a. Provide a **comprehensive narrative** describing the **research methods**.

- 1) Provide the **order in which tests/procedures will be performed**,
- 2) Provide the **setting** for these events and a description of the **methods used to protect privacy** during the study.
- 3) Provide the **plan for data analysis** (include as applicable the **sample size calculation**)

Please respond to all components of this item, or clearly indicate which components are not applicable.

**Data Tracking and Storage.** All survey data will be captured, stored, tracked, and analyzed via Research Electronic Data Capture (REDCap), a secure, web-based application for research data.

**Randomization and Scheduling:**

Study coordinator (SC) will monitor referral queue daily

Randomization software (<http://abtesting.ideas42.org/randomize/>) will be used to randomize patients in the referral queue to each study arm (in-person genetic counseling or IPGC/ telephone genetic counseling or TGC). Patients who meet the following exclusion criteria will not be randomized to a study arm. Patients who are excluded from the study will be scheduled for an appointment as per normal clinic protocol by the clinic schedulers.

SC will monitor number of participants per study arm and adjust recruitment accordingly.

Patients who have been randomized to a study arm will be scheduled for IPGC or TGC by schedulers at John Peter Smith (JPS) and Parkland Hospital (PHHS). Schedulers will inform patients of their appointment as per normal clinic protocol. Spanish-speaking patients will be contacted with an interpreter.

Patients who elect alternative service delivery model for genetic counseling than what was assigned after randomization will be excluded from the study. The genetic counseling appointment type will be modified based on patient preference and patient will continue with scheduled visit, but not as part of the study.

SC will record the following data for all referred patients in Research Electronic Data Capture (RedCap), a secure, web-based application for research data: MRN; study arm assigned; genetic counseling appointment date; if patient was excluded from study, and reason for exclusion. The following demographic data will also be tracked: patient's age; patient's sex; patient's race and ethnicity; patient's preferred language; patient's contact information (phone number and e-mail address)

**Study Eligibility Determination and Informed Consent.** One week prior to scheduled genetic counseling appointment, SC will call patient to assess if patient meets study eligibility criteria. Spanish-speaking patients will be contacted with an interpreter.

If SC cannot reach the patient, SC will make second contact attempt the following business day.

Scheduled patients who cannot be reached or do not call back will be excluded from study.

SC will record the following data in RedCap: contact date and outcome; if eligibility criteria were met; if patient was excluded from study, and reason for exclusion.

If patient qualifies for study, SC will describe study protocol and get verbal consent for study participation using the consent script. All patients will be sent a hard copy of the consent document for their records (available in English and Spanish) electronically along with the study surveys via RedCap.

Patients who decline will be excluded from study. Study participation status will be recorded in RedCap (including reason for declining participation).

Patients who decline to be in the study will be sent an appointment letter and will continue with scheduled genetic counseling appointment as per normal clinic protocol, not as part of the study.

**Pre-Appointment Resources and Survey Completion.** Patients who agree to participate in the study will be sent the pre-appointment survey (Appendix B). A Spanish version of the survey will be sent to Spanish-speaking patients. Surveys will include a hard copy of the consent document that can be downloaded as desired. Survey links will be sent to patients via email. All surveys will be available through REDCap.

The pre-appointment survey will consist of the Multi-dimensional Model of Informed Choice (MMIC) assessment and the Genomics Outcome Scale (GOS).

SC will check pre-appointment survey completion status two business days prior to appointment.

Patients with incomplete pre-appointment surveys will be contacted two business days prior to appointment and will be reminded to complete survey. Patients will be offered the option to complete survey via telephone with SC. Spanish-speaking patients will be contacted with an interpreter.

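### Recruitment may be adjusted by arm count at the coordinator's discretion, with no rule that keeps assignment random or recruitment effort equal

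*Combined protocol and SAP*

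**What the plan says.** Section 3 describes the design: "This is a two-arm parallel randomized controlled study of IPGC vs. TGC with two enrolling sites". In Section 4.a, under Randomization and Scheduling, a web-based tool "will be used to randomize patients in the referral queue to each study arm". Shortly afterwards comes the sentence at issue: "SC will monitor number of participants per study arm and adjust recruitment accordingly".

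The plan does not say which count is monitored (randomised, consented or complete), what is adjusted, when, by what rule, or with whose approval. Section 4.a describes no blocking, stratification, pre-generated list or allocation concealment.

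The same coordinator watches the referral queue and records the assigned arm. One week before the appointment, when the arm is already set, the coordinator makes the eligibility call and then seeks verbal consent.

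The sample size paragraph of Section 4.a covers extension of accrual separately and without reference to arm. It states "We plan to enroll 280 patients at a 1:1 ratio per arm (100 individuals enrolled per arm), expecting 200 to complete measured responses", and says that the team will "adjust accrual for study-specific dropout until we have 200 participants' complete measured responses".

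**The concern.** Randomisation supports all three primary comparisons (satisfaction, knowledge and visit completion). Here the trigger for action is the running count in each arm, and the person acting knows each patient's arm. Two ways of carrying out the sentence would harm the comparison:

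- Close a full arm or change the ratio. Late assignments then become deterministic or predictable, and calendar time is confounded with arm.
- Keep assignment random but try harder to reach and consent patients in the shorter arm. Selection after randomisation then differs by arm.

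Unequal counts are plausible. Section 1 expects higher visit completion with TGC, and patients who switch model, cannot be reached, decline or leave surveys incomplete are excluded after assignment. The sentence is therefore likely to be used. If the adjustments are not recorded, the analysis cannot undo them.

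**Working it through.** **1. The plan's own figures.** Inputs from the sample size paragraph and Table 1: detectable difference 0.398 SD, 80% power, two-sided 0.05, 100 per arm, 30% dropout, visit completion 63% against 81.6%.

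- Means: n per arm = 2 × (1.960 + 0.842)² / 0.398² = 99.1, so 100. Power at 100 per arm is 0.804 (normal approximation) or 0.800 (t distribution). The plan's figure reproduces.
- Visit completion: 90 per arm without continuity correction and 101 with it, in line with 100.
- Dropout: 200 / 0.70 = 285.7, so 286 against the 280 stated, which is close.

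No stated number is wrong on this point.

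**2. Readings of the sentence.**

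| Reading | Assignment | Effect |
|---|---|---|
| (a) Randomise 1:1 throughout, change total accrual | random | none |
| (b) Close a full arm or change the ratio | late patients not random, or predictable | allocation bias, confounding with time |
| (c) Vary contact or consent effort by known arm | random | selection after randomisation |

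Reading (a) is already provided for in the sample size paragraph, which makes no mention of arm. The sentence in Randomization and Scheduling adds the arm count as the trigger. Nothing in the text excludes (b) or (c).

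**3. Illustrative size under (b).** Assumed rule, not in the documents: simple 1:1 randomisation until one arm has 100 completers, then every later patient goes to the other arm. The retention splits are also assumed, and only the average of 70% follows from the plan. Simulation with 20,000 runs per row:

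| Retention IPGC / TGC | Completers placed without chance, mean (5th–95th percentile) | Assigned patients placed without chance, mean |
|---|---|---|
| 70% / 70% | 11 (1–26) | 16 |
| 65% / 75% | 16 (2–33) | 24 |
| 60% / 80% | 25 (6–43) | 42 |

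Check on the first row: with equal retention the expected shortfall is 200 × C(200,100) / 2²⁰⁰ = 11.27 completers, and 11.27 / 0.70 = 16.1 assigned patients. Check on the last row: when TGC reaches 100 completers, IPGC has about 100 × 0.60/0.80 = 75, which leaves 25, and 25 / 0.60 = 42 assigned. As shares of 200 completers, 11 to 25 is about 6% to 13%.

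**4. What balancing would gain.** For a fixed total, the detectable difference is proportional to √(1/n₁ + 1/n₂).

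- A 113:87 split is what 200 completers would give if retention were in the ratio 81.6:63 (200 × 81.6/144.6 = 112.9). Then √(1/113 + 1/87) = 0.1426, against √(2/100) = 0.1414 for 100:100. The ratio is 1.0086, so 0.398 becomes about 0.402 SD.
- Simple randomisation of 200 has a 95% range of 86 to 114 per arm. At 86:114, power for 0.398 SD is 0.796 against 0.804. For visit completion it is 0.838 against 0.842 (no continuity correction).

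**The case against.** The strongest reply is that the text speaks of recruitment, not assignment. It never withdraws the software randomisation, the ratio stays 1:1, and watching counts is ordinary trial conduct. Reading (a) is harmless and fits the words. The study scheme in Section 3 is also not visible in the text available, so any allocation detail shown there could not be checked. This stands as far as it goes: the plan does not say that the coordinator chooses or overrides assignments.

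A reader might therefore go too far in two ways.

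- One might conclude that the arms are no longer randomised. That follows only under reading (b), which the documents permit but do not state.
- One might put the size at about 36 patients, from 100/0.63 = 158.7 IPGC and 100/0.816 = 122.5 TGC assignments. That needs a rule of filling each arm to 100 attenders, which is not in the plan; the accrual target is completed responses. It also treats 81.6% as an expected rate, whereas the sample size paragraph offers it only as an example of a detectable difference.

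It is also fair to say that randomising before the eligibility and consent call opens a route to selection with or without this sentence. Removing the sentence would not close that route.

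What remains is that the trigger is arm-specific, the discretion has no stated limit, its holder knows the arm, and the separate provision for extending accrual already covers the harmless use.

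**Conclusion.** The concern holds as a gap in the safeguards, not as a finding that randomisation is broken. The plan allows recruitment to respond to arm counts at the discretion of a coordinator who knows the assignment, and no rule keeps assignment random or effort equal. The arms may therefore lose comparability.

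The figure of roughly 11 to 25 of 200 completers is illustrative. It rests on the assumed filling rule and on assumed retention of 70%/70% to 60%/80%. The resulting bias cannot be estimated from the documents, because it depends on how late patients differ from earlier ones.

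Against that risk there is almost no statistical gain: at most about 0.004 SD in detectable difference at 113:87, or under one percentage point of power at 86:114. The sentence should be changed.

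**What to change.** Replace the sentence in Randomization and Scheduling with wording such as:

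*Counts per arm may be monitored, but any adjustment changes only the total number randomised. Every assignment comes from a concealed, pre-generated 1:1 list in permuted blocks (for example stratified by site) until accrual ends. Contact and consent procedures are identical in both arms.*

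Monitoring itself can stay. The dropout review after the first 50 responses can also stay, provided that it alters only the total. Stratifying by site is an option, since there are two sites, and is not essential to the correction.

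The cost is a protocol wording change and one pre-generated list. The order of assignment, eligibility call and consent need not change for this fix. The small downside is that completer counts may differ between arms, with the negligible loss of precision shown above.
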